therapy, speech therapy, nursing, medical assessment and intervention, and transportation costs of patients/carers to and from day hospital centres; and of health care professionals to and from patients' homes; use of special aids and equipment; introduction of home alterations; personal care received through rehabilitation service. The provision of social and personal services which do not contribute directly to the rehabilitation process is excluded from the evaluation of these packages of care. However, they will be considered within the economic evaluation:

Information on personal and social services received at home will be collected through interviews (see below); information on personal and social services provided in day hospital will be monitored in each centre.

To estimate the use of resources made by the rehabilitation team, service elements will be recorded for each patient in a proforma. These will include date of visits, job title of the health care professional(s) seen on that day, the grade, the length of visit, the mileage per patient. The total time per patient will be the time spent on all service elements for that patient. This will allow to estimate labour costs. All material items/ equipment used during each action will be also be recorded. Fixed costs, such as overheads and general costs will be allocated pro-rata according to relevant parameters such as floor area used, number of staff, throughput.

Estimation of subsequent use of resources. Use of services - other than those included as part of the packages of care - to be monitored in both patient groups via questionnaire include: outpatient visits and hospitalisations, investigations, A&E admissions, use of ambulance services, visits and telephone consultations to and from the general practitioner and any other health care professionals, use of medications, personal and social services, attendance to day care centres, short-term respite or permanent care.

Details on procedures/investigations undertaken in hospital (eg, during hospitalisation or casualty attendance) will be extracted from patients' records, at 3, 6, 9, 12 months post-randomisation, as well as being including in questionnaire, to double check. Records will be reviewed over the previous three months.

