Data on the use of all the other services/resources will be collected through questionnaire interviews to the patients. The interviews will be carried out at 1, 3, 6 and 12 months post-randomisation. Patients will be asked which services they used, and how often, over the previous month. Manpower data will be collected separately for each main category of staff. Moreover, the interview will collect information on the patients' expenditures due to travel, use of any equipment/special aids, changes introduced to accommodations/living environments, private medical/paramedical visits, assistance received by informal caregivers, any other out-of-pocket expenditures. Whenever practically feasible, patients will be asked to provide details for their financial expenditures and quantities separately.

Data collection instruments (hospital, patients and carers) have been prepared adapting those used in a randomised controlled trial on cardiac pacemaking of older people being carried out at CHSR, University of Newcastle(22). Questions on modifications of living environments have been adapted from a questionnaire used in a study of early supported hospital discharge for stroke(23). Questionnaires have been prepared thinking of the clinical management strategies and event pathways.

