2	In the last 8 weeks, have you been seen in an outpatient department at a hospital because of your condition or other health reasons? Please do not count the times you went there for tests/investigations only, I will ask you about these later. Only count those in addition to your rehabilitation treatment. Can you remember which hospital/clinic departments you have been seen as an outpatient? I will also ask you how many times this has happened. I have a list, which might help you.	
a)	Have you been seen in a geriatric department? Yes 1 no. times   No 2	21 22
b)	Have you been seen in an orthopaedics department? Yes 1 no. times   No 2	23 24
c)	Have you been seen at a rehabilitation/physiotherapy department? Yes 1 no. times   No 2	25 26

d)	Have you been seen at a generic medical department?	27
	Yes 1 no. times   No 2	28
e)	Have you been seen at a neurology department?	29
	Yes 1 no. times   No 2	30
f)	Have you been seen at an ophthalmologist department?	31
	Yes 1 no. times   No 2	32
g)	Have you been seen at an ENT department?	33
	Yes 1 no. times   No 2	34
h)	Have you been seen in an Accident and Emergency department?	35
	Yes 1 no. times   No 2	36
i)	a) Have you been seen in any other department?	37
	Yes 1 Specify where.....no. times   No 2	38

3	In the last 8 weeks, have you had to stay in hospital as a day patient or overnight because of your condition or other health reasons? (RECORD GENDER OF PATIENT). 
Yes (1) No (2)
 If yes ask name of hospital.....	39
4	In the last 8 weeks, did you have any tests/investigations because of your condition or any other health reasons? Please do not count those you have had while admitted to hospital or those you have had during the outpatient visits you reported earlier on. I have got a list of tests and investigations some people might have had. You may be familiar with some of the words, but don't worry if you do not recognise all of them. Can you please tell me if you have any of the following and how many times? Ring all that apply	

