16	Because of your condition or other health reasons have you had to either rent new accommodation or sell your house since in the last 8 weeks? Yes (1) No (2) If no skip to question 19	291
17	Has this caused a financial loss to you or your family? Yes (1) No (2) If yes how much was the loss? £.....	292 293
18	How much did it cost you to move your furniture and personal things? £.....	294
19	In the last 8 weeks, have you moved into residential/nursing home or made use of day care centres/sitting services at home because of your condition or other health reasons? Yes (1) No (2) If no skip to question 22	295
	How many days in the last 2 months? Permanently	296
	Short stay	297
	Day care centre	298
	Sitting services	299
20	Do you pay personally for you to stay in residential/nursing care or make use of day care centre/sitting services? Yes (1) No (2) If no, who pays?.....	300
21	How much are your bills monthly? £.....	301

22	In the last 8 weeks, did you have to meet any travel costs because of your condition or other health reasons (e.g. to attend clinical appointments, or to get the prescribed treatment/equipment)? Yes (1) No (2) If no skip to question 26	302
23	Can you please provide as much information as you can about the travel	

ts you had to meet because of your condition or other health reasons? ease include costs for return journeys).
														

Can you tell me how you travelled?
 
Tick=1 No tick=2
	
Please tick all that apply.
	
How many miles did you travel overall
 
(If you can't remember exactly, can you please estimate it)
												
		
How much did these journeys cost you altogether?
 
(If you can't remember exactly, can you please estimate it)
												
		
 
 £	p	
 
 		
 
 		
 
 		
 
 		
 
 		
 
	£	p										
£	p													
By train/metro														
By bus														
By private car														
By taxi														
		303 304 305												
		306 307 308												
		309 310 311												
		312 313 314												
24	
If you travelled by car, did you have to pay any tolls or parking fees?
 
Yes (1) No (2)
 
If no skip to question 26
	315												
25	
How much did you pay for tolls or parking fees?
 
£.....
	316												

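### Questionnaire item Q3 records only whether a hospital stay occurred and where, so the questionnaire cannot give admissions or bed-days, and the record review is not specified to supply them

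*Protocol*

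**What the plan says.** Under Resource data collection and costing methods, the paragraph on subsequent use of resources names the services "to be monitored in both patient groups via questionnaire include: outpatient visits and hospitalisations, investigations, A&E admissions" and others. Hospitalisations are therefore assigned to the questionnaire. The same section sets out what the interview is to obtain: "Patients will be asked which services they used, and how often, over the previous month".

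A second source is patient records, reviewed at 3, 6, 9 and 12 months after randomisation, each time over the preceding three months. Its content is given as: "Details on procedures/investigations undertaken in hospital (eg, during hospitalisation or casualty attendance) will be extracted from" those records, with the questionnaire serving as a double check. The next paragraph leaves the rest to the interview: "Data on the use of all the other services/resources will be collected through questionnaire interviews to the patients".

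In the appended Economic Questionnaire for patients, Q3 uses an 8-week recall period and asks: "have you had to stay in hospital as a day patient or overnight because of your condition or other health reasons". The answer is Yes (1) or No (2), coded in field 39, and the only follow-up is "If yes ask name of hospital".

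**The concern.** The text promises frequency, but the form does not ask for it. Q3 gives the share of patients with at least one stay in the window. It does not give the number of stays or the nights, and it does not separate a day case from an overnight admission.

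This matters because cost can decide the trial's recommendation. Lower cost of home rehabilitation is one of the stated hypotheses. Under Synthesis of costs and benefits, if neither setting is shown to be more effective, the cheaper one is to be recommended. The costing method multiplies unit costs by the volume of resources used, and Q3 supplies no volume for inpatient care. The protocol also expects skewed costs and asks for arithmetic means, which depend on the few patients with long stays. No later analysis plan can recover a quantity that was not recorded.

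**Working it through.** The protocol states no figure on this point, so the check compares the stated data sources with the form.

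**1. Does the form collect frequency elsewhere?** Yes.
- Q1, Q2, Q4, Q5, Q6 and Q7 each have a box for number of times. The A&E item in Q2 ("Have you been seen in an Accident and Emergency department") is one of them.
- Q19, on residential and day care, asks "How many days in the last 2 months".
- Q3 has neither a count nor days.

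**2. Could a count box have been lost from the text?** This is unlikely. The field codes run 38 (last part of Q2), 39 (Q3), 40 (first part of Q4), so no coded field is missing at this place. Q3 also carries a stray instruction to record the patient's gender, which is asked again at Q36. That is consistent with an editing slip.

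**3. Does another item capture stays?** No. Q4 tells the patient to leave out tests done while admitted, and no other field concerns hospital stays.

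**4. Does the record review capture them?** It covers the right period: 4 reviews x 3 months = 12 months. Its stated content is procedures and investigations. Number of admissions, admission and discharge dates, and length of stay are not named. The pre-pilot decision to check notes gives tests as its example. Table 5 mentions checking against medical records for NHS transport and medication, but not for use of health and social services.

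**5. What does a Yes mean?** The window is 8 x 7 = 56 days. A Yes fits 0 nights (one day case) up to about 56 nights, in one stay or several.

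**6. What is lost if each Yes receives one average cost?** Let p be the proportion answering Yes, and let m and s be the mean and standard deviation of nights among them, using a simple model for one window.
- Mean nights per randomised patient = p x m. With one common m, a difference in p between arms is kept and a difference in m is lost.
- The true variance of nights per patient is p x s² + p(1 - p) x m². With one fixed value per Yes, only p(1 - p) x m² remains. The term p x s², which carries the long stays, disappears. The interval for the cost difference is then too narrow even if mean stays are equal.

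**7. Illustration only.** The documents give neither p nor any difference in m, so both are assumed. Take equal p in both arms and a gap d in mean nights:
- p = 0.20, d = 12 - 8 = 4: 0.20 x 4 = 0.8 bed-days per patient per window unseen by Q3.
- p = 0.10: 0.10 x 4 = 0.4. p = 0.30: 0.30 x 4 = 1.2.
- d = 0: no difference in means is lost, only the variance in step 6.

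These values show the mechanism. They do not estimate this trial's bias.

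**The case against.** A reader might infer that hospital stays cannot be counted or costed at all in this trial. The documents do not support that. The record review spans the full 12 months and expressly reaches hospitalisation episodes. Staff cannot extract what was done during an admission without identifying that admission in the notes, and the hospital name in Q3 may be meant to locate it. No word in the text closes the review to other items. This stands, and it limits the point to what the questionnaire can give and what the review is specified to take. It does not close the gap, because a site could complete both instruments exactly as described and still hold no admission count or dates.

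A reader might also infer that every difference in inpatient use disappears. It does not: if more patients in one arm are admitted, the proportion answering Yes shows it.

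A third tempting reading is that Q3 will count day hospital rehabilitation attendances as stays in one arm. The questionnaire's introduction already restricts it to services additional to rehabilitation. Q1, Q2 and Q7 repeat that restriction and Q3 does not, so a reminder is worth adding, but the exclusion is not absent.

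The protocol's Literature section reports a systematic review that found a day hospital advantage in hospital bed use unlikely. This tempers the difference to be expected between arms. It does not establish equality here, and it does not restore the lost variance.

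Finally, the form is visibly rough. Some field numbers repeat or are skipped later on, and its 8-week recall and interview times differ from the text. It may not be the final version. That is a reason to correct it now.

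**Conclusion.** The point holds in this form. The protocol makes the questionnaire the source for hospitalisations and promises frequency, but Q3 delivers only whether and where a stay occurred. The record review could supply the rest, but its stated items do not include admissions or length of stay. As written, neither source is set to provide the volume of inpatient care that the costing method needs.

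Among patients answering Yes, differences between arms in number or length of stays would be lost, and so would the long-stay part of the cost distribution. A difference in the proportion with any stay would be kept. The effect on the cost comparison could go in either direction. Its size cannot be derived from the documents, and the 0.4 to 1.2 bed-days above are assumed values for illustration. The conclusion rests on the printed form being the one used and on the record review taking only the items named. It should be settled before data collection, because it cannot be repaired afterwards from the questionnaire.

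**What to change.** 1. In Q3, record the number of day-patient episodes separately from overnight admissions, and for overnight admissions record the number and the total nights. Keep the hospital name.
2. Repeat in Q3 the instruction, already in the questionnaire's introduction, that rehabilitation attendances are not counted.
3. In the paragraph on record extraction, name admission and discharge dates as items to be taken at the reviews already planned for 3, 6, 9 and 12 months. State that these dates are the source for bed-days, with Q3 as the cross-check.

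The cost is a few extra fields on the form, a slightly longer interview for patients who were admitted, and two dates per admission in a review that is already planned.

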a)	Blood tests 
Yes (1) No (2) no. times 
	40 41
b)	Urine test 
Yes (1) No (2) no. times 
	42 43
c)	X-ray 
Yes (1) No (2) no. times 
	44 45
d)	CT (computerised tomography) brain scan	46

	Yes (1) No (2) no. times  	47
e) MRI (magnetic resonance imaging) brain scan	Yes (1) No (2) no. times  	48 49
f) ECG, Heart tracing	Yes (1) No (2) no. times  	50 51
g) Ultrasound	Yes (1) No (2) no. times  	52 53
h) EEG (brain wave recording)	Yes (1) No (2) no. times  	54 55
i) Other (SPECIFY):	Yes (1) No (2) no. times  	56 57
j) Other (SPECIFY):	Yes (1) No (2) no. times  	58 59

5	In the last 8 weeks, have you used an emergency ambulance service because of your condition or any other health reasons? Can you please remember the number of times? (please count journeys both to and from the hospital as separate journeys) Yes (1) No (2) no. times  	60 61
6	In the last 8 weeks, have you used a pre-booked NHS transport service (e.g. minibus, ambulance, taxi) because of your condition or any other health reasons? Can you please remember the number of times? (please count journeys both outwards and inwards journeys as separate journeys) Yes (1) No (2) no. times  	62 63

	Now I will ask you about visits you have received at home through the NHS or the social services.	
7	In the last 8 weeks, have you received any visits at home because of your condition or other health reasons and can you remember how many times? Please do not include the visits you have had as part of your rehabilitation treatment since we will get this information from the Centre.	
a)	Have you been seen by your GP or another doctor at home? Yes (1) No (2) no. times  	64 65
b)	Have you been seen by a health visitor at home? Yes (1) No (2) no. times  	66 67

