c)	Have you been seen by a social worker at home? Yes (1) No (2) no. times  	68 69																								
d)	Have you been assisted by a home carer? Yes (1) No (2) no. times  	70 71																								
e)	Have you been seen by a disablement resettlement officer at home? Yes (1) No (2) no. times  	72 73																								
f)	Have you been seen by a psychologist at home? Yes (1) No (2) no. times  	74 75																								
g)	Have you been seen by a counsellor at home? Yes (1) No (2) no. times  	76 77																								
h)	Have you been seen by a district nurse at home? Yes (1) No (2) no. times  	78 79																								
i)	Have you been seen by some other person at home? Yes (1) No (2) no. times  	80 81																								
j)	Have you received meals on wheels? Yes (1) No (2) no. times  	82 83																								
8	In the last 8 weeks, have you seen anybody privately (e.g. at your expenses or through a private insurance scheme) because of your condition or other health reasons? Yes (1) No (2) If no skip to question 10	84																								
9	Who have you seen privately? Tick=1 No tick=2 Fill in the second column first, then fill in each applicable row 
  
 	(TICK ALL THAT APPLY).	How many times did this happen since in the past 8 weeks.	How much did it cost altogether? £	
   
 A physiotherapist				
 
 A speech therapist				
 
 A chiropodist				
 
 An occupational therapist				
 
 An osteopath				
  
		(TICK ALL THAT APPLY).	How many times did this happen since in the past 8 weeks.	How much did it cost altogether? £	A physiotherapist				A speech therapist				A chiropodist				An occupational therapist				An osteopath				85 86 87 88 89 90 91 92 93 94 95 96 97 98 99 100 101 102

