26	
In the last 8 weeks, did you have any other extra expenses because of your condition or other health reasons (e.g. purchase of books or videos about your condition)?
 
Yes (1) No (2)
 
If no skip to question 28
	317												
27	
If yes, please tell me the item and how much you have spent on each item:
 
Item 1:
 
Description of item.....
 
Amount spent.....
	318												
	
Item 2:
 
Description of item.....
 
Amount spent.....
	319												

28	
In the last 8 weeks have you received any assistance at home to help in your personal care or home care because of your condition or other
	320
-----------	--	-----

	health reasons? Please exclude the visits through the NHS and social services you have already mentioned earlier on.							
						Yes (1)	No (2)	
	If no please go to question 30							
29	If yes, who helped you?							
	Partner/Spouse (1)	Relative (2)	Friend (3)	Nurse (4)	Paid Home carer (5)	Other e.g. grand child(6)	Other (6)	321 Helper 1 322 Total hours
Tick								323 Cost
For how long in total?								324 Paid by Patient – 1 Other – 2
Days								325 Helper 2 326 Total 327 Hours
Hours								328 Cost
Minutes								329 Paid by Patient – 1 Other – 2
Total cost	£	£	£	£	£	£	£	330 Helper 3 331 Total hours
Paid by? (Tick)								332 Cost
Patient								333 Paid by Patient – 1 Other - 2
Other (please state)								

30	Now I will ask you a few questions about your work. If you are retired, please answer these questions about your last main job . If the patient has never worked please tick this box and skip to question 32 	Tick = 2 No tick=1
	a) What is your job title?	334
	b) What do/did you actually do?	
	c) What does the firm or organisation you work(ed) for make or do?	
	d) Are/were you?: An employee 1 or self-employed..... 2	335
	e) Are/were you a manager, foreman or supervisor of any kind? Yes, manager..... 1 Yes, supervisor..... 2 No, neither..... 3	+336
31	Because of your condition or other health reasons have you done any of the following in the last 8 weeks? Gone on sick leave? 1 Gone on long-term sickness benefit(s)? 2 Retired early from work? 3 Given up work altogether? 4 Already retired? 5	337

	None of these happened? 6	

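### Publicly provided home care (Q7d) is counted but not timed, and its two-box count may be too small, so its cost can only be approximated

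*Protocol*

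**What the plan says.** The economic questionnaire for patients introduces Q7 with "Now I will ask you about visits you have received at home through the NHS or the social services" and sets the recall period: "In the last 8 weeks, have you received any visits at home". Within Q7, item d reads "Have you been assisted by a home carer? Yes (1) No (2) no. times", followed by two entry boxes. It has no field for minutes, hours or cost.

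Help at home from other sources is taken at Q28 and Q29. Q28 tells the patient: "Please exclude the visits through the NHS and social services you have already mentioned earlier on". Q29 then asks "For how long in total", with rows for days, hours and minutes, total cost and payer. Its columns run from spouse and relatives to a paid home carer.

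The Economic Evaluation section (estimation of subsequent use of resources) lists the services to be monitored by questionnaire, including "use of medications, personal and social services, attendance to day care centres, short-term respite or permanent care". The same section makes the interview the source for personal and social services received at home. On recall, it says "Patients will be asked which services they used, and how often, over the previous month", which is not the 8 weeks printed on the form.

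**The concern.** One kind of care is measured in two ways, depending on who provides it. A privately arranged home carer is timed and costed at Q29. A carer provided through the NHS or social services is only counted at Q7d. A short check and a long personal-care visit both enter as one.

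Two of the protocol's aims depend on this item. One hypothesis is that home-based rehabilitation (HBR) is less costly than day hospital rehabilitation (DHR). The Economic Evaluation includes costs to providers of social services under its societal perspective. Home care is a recurring cost, and its use could plausibly differ between the arms. The section on synthesis of costs and benefits adds that, if neither strategy is shown to be more effective, the cheaper one per patient will be recommended. Error in a recurring cost can therefore reach the conclusion.

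The size of the count field is a second, lesser worry. Costs are expected to be skewed and are to be compared on arithmetic means, so a field that cannot hold the heaviest users' counts would lose the part of the distribution that weighs most on the mean.

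**Working it through.** The protocol states no home-care volume or field capacity, so there is no figure to reproduce. The check has three parts.

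**1. Could another source supply visit length?**
- Q29: no, because Q28 excludes these visits.
- Q19: it covers days in residential care, day care and sitting services, not time from a home carer.
- Staff proforma: it records length of visit, but for the rehabilitation team only.
- Record checks: Table 5 checks NHS transport and medication against records; the Economic Evaluation text extracts hospital procedures and investigations. Neither covers home care.
- Carer questionnaire: it asks weekly hours of the interviewed carer only. It lists a paid carer as a possible relationship, but the protocol directs that interview at informal carers.

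**2. What does a count without length leave open?** Hours = visits × minutes per visit ÷ 60. Visit lengths here are assumptions; the protocol gives none.
- 56 visits (one a day for 56 days): 56 × 15 ÷ 60 = 14 hours; 56 × 60 ÷ 60 = 56 hours.
- 112 visits (two a day): 112 × 15 ÷ 60 = 28 hours; 112 × 60 ÷ 60 = 112 hours.

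The same count covers a fourfold range of hours. For the comparison of arms, suppose both average 56 visits, with 30 minutes a visit in one arm and 45 in the other. True use is 28 and 42 hours, yet the form shows no difference. If length is the same in both arms, a wrong assumed length rescales the home-care difference but does not change its sign.

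**3. When would the count overflow?** If each box holds one digit, the maximum is 99. The form does not state this. The carer questionnaire's date of birth, with six boxes for day, month and year, supports the reading. The threshold over 8 weeks is 99 ÷ 56 = 1.77 visits a day.

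| Visits a day | 7 days a week, 56 days | Share lost if cut at 99 | Weekdays only, 40 days | One-month recall, 30 days |
|---|---|---|---|---|
| 1 | 56, fits | none | 40, fits | 30, fits |
| 2 | 112, overflows | 1 − 99/112 = 12% | 80, fits | 60, fits |
| 3 | 168, overflows | 1 − 99/168 = 41% | 120, overflows | 90, fits |
| 4 | 224, overflows | 1 − 99/224 = 56% | 160, overflows | 120, overflows |

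Twice-daily care on 49 of the 56 days gives 98 and fits; on 50 days it gives 100 and does not. Visit frequencies are also assumptions.

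**The case against.** A reader might infer that the cost of public home care cannot be measured at all. The protocol does not support that. Its costing methods mix microcosting with gross costing and draw on national averages and, where needed, local NHS and social service accounts. A count multiplied by an average cost per visit is a cost. The sensitivity analysis is also meant to make simplifying assumptions explicit, and an assumed visit length is one of these. What remains is that varying an assumed length cannot recover a difference between arms that was never recorded.

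A reader might also infer that the item pulls the arm difference towards zero and so favours HBR. That does not follow. Missing length can hide or create a difference only if length differs between arms, and the protocol gives no evidence that it does. The cap alone would attenuate a difference, and it could as easily hide a home-care saving under HBR as an increase.

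The overflow is open to challenge too. One digit per box is inferred, an interviewer could write a larger number beside the boxes, and nothing says values are cut at 99. The percentages assume truncation and seven-day care throughout, and the share of patients with such use is unknown. This limits the overflow to a secondary point. The missing length does not depend on it.

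Finally, the core economic analysis is centred on the health service budget, and the protocol wants to keep its instruments from becoming burdensome; Table 4 gives 360 questions for the patient economic questionnaire. Both are fair and limit the importance of the point. They do not remove it, because the societal analysis is also a stated aim and the extra question would go only to patients who report a home carer.

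**Conclusion.** The point holds as a measurement weakness that is cheap to correct. Q7d takes a count of publicly provided home-carer visits and no length, and no other planned source fills the gap. The cost of this care must rest on an assumed average visit length, with a fourfold range in hours if visits last 15 to 60 minutes, and a difference in length between arms is invisible.

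The count field is a lesser defect and depends on reading each box as one digit. It then fails for care of two or more visits a day given on all, or nearly all, of the 56 days (112 against 99). Twice-daily weekday care fits, and under a one-month recall overflow would not begin until four visits a day.

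The effect falls mainly on the societal and social-services cost comparison. Neither the direction nor the size of any bias in the arm means can be derived from the protocol.

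**What to change.** - In Q7d, for patients who answer yes, record visits per week and usual minutes per visit, or total time in the layout Q29 already uses. Visits per week also removes the overflow: four a day is 4 × 7 = 28.
- Where a total count over the recall period is kept for a service that can exceed once a day (home carer, district nurse), allow three digits; 112, 168 and 224 then all fit.
- Reconcile the 8-week recall on the form with the previous month given in the Economic Evaluation text. The two imply different volumes and different overflow points.

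This changes one or two items and one sentence of text. The burden is about one extra minute for patients who receive home care and none for the rest. It should be done before data collection, since the length of past visits cannot be reliably reconstructed after follow-up.
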